## **6.2 Demographics and Baseline Characteristics**

The variables listed in section 5.1 and 5.2 will be described and analyzed between the two treatment groups according to the general methodology in section 6.1 above. These analyses and tables will be given for both the ITT and PP population.

## **6.3 Efficacy Analyses**

### **6.3.1 Primary efficacy analysis**

In this non-inferiority study the primary efficacy analysis will be constructing a two sided 95% confidence interval, using Fisher's non-parametric permutation test, for between-treatment differences (Exufiber® - Aquacel® Extra) in the mean percentage wound area reduction from baseline to 6 weeks follow-up using PictZar on the PP population. A corresponding complementary two sided 95% confidence interval on the ITT population will also be constructed. If the lower limits of both these confidence intervals are greater than 12% non-inferiority will be established.

For the primary efficacy endpoint last observation carried forward will be applied for the last follow-up measurement before 6 weeks and forward to the final 6 week measurement. Supporting identical analyses will be performed on the primary efficacy variable using the values from a second supportive blind review of the independent French expert.

Also a sensitive analysis using PictZar will be performed using complete cases.

Tables will be given for wound area by visit and analysed between treatments and for wound area reduction (%) from baseline to each visit and analysed between treatments.

Superiority can be concluded if the lower bound of a two sided 95% confidence interval for between-treatment differences (Exufiber® - Aquacel® Extra) in the mean percentage wound area reduction from baseline to 6 weeks follow-up using PictZar on the ITT population does not overpass zero.

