#### 4.6.4 Efficacy Measurements and Variables

See appendix C for details.

The primary endpoint will be

- Relative reduction of wound area (%) from baseline to end of investigation (up to 6 weeks) measured by the validated system PictZar on the photos taken after debridement at week 0, week 4 and week 6 (or final visit).

Secondary endpoints are to evaluate;

- Wound area reduction (absolute change in cm^2) from baseline to end of investigation (up to 6 weeks). Also measured by PictZar.
- Linear advance of the wound margin according to Gilman's formula (Cardinal et al, 2008) based on the digital photos and calculated by PictZar
- Relative reduction of fibrin/sloughy tissue after the 6-week treatment period or when the wound is dry/healed. (Measured with PictZar and according to the judgment of the clinician)
- Debrided wound at end of investigation

- ✓ at least 70% of the wound surface area covered with granulation tissue confirmed using PictZar
- Changes from baseline in the condition of the peri-wound skin measured by the following variables; maceration, redness/irritation, blistering, skin stripping, trauma to wound edges
- The level of pain in connection to dressing changes and during debridement (measured by visual analog scale 0-100mm)
  - ✓ Any intake/application of analgesics within 3 hours?
  - ✓ Pain before dressing assessment
  - ✓ Pain DURING dressing removal
  - ✓ Pain during debridement
- Cost effectiveness and health economics will be measured using EQ-5D-3L and dressing material used
- No of dressing changes per week and during the total treatment period
- Wound status
  - Exudate amount and nature
  - Wound bed aspect before and after debridement/cleansing
    - ✓ % of fibrin/sloughy tissue
    - ✓ % of granulation tissue
    - ✓ % of epithelialization
    - ✓ % other
- Clinician's opinion in relation to the dressing
  - ✓ Ease of application of the dressing
  - ✓ Ease of removal of the dressing
  - ✓ Non-adherence to wound bed at removal of primary dressing
  - ✓ Non-adherence to peri-wound skin at removal of primary dressing
  - ✓ Flexibility of dressing
  - ✓ Overall experience of the dressing
  - ✓ Conformability to the wound
- Subject's opinion in relation to the dressing
  - ✓ Experience anxiety during study product change

- ✓ Ease of movement while wearing study product
- ✓ Study product remained in place while wearing it
- ✓ Sting or burning while wearing study product
- ✓ Comfortable to wear

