## **4.8 Statistical Methods and Determination of Sample Size**

### **4.8.1 Statistical Evaluation**

The intent-to-treat (ITT) population is defined as all randomised patients with at least one follow up planimetry value (from the validated tool PictZar) and the per-protocol (PP) population as all patients with a wound area measurement till the fourth week of follow-up, at least. Subjects with significant protocol deviations will be excluded from the PP population.

PictZar has received 510k notification and is compliant with CFR Part 11.

In this non-inferiority study the primary efficacy analysis will be constructing a two sided 95% confidence interval, using Fisher's non-parametric permutation test, for between-treatment differences (Exufiber® - Aquacel® Extra) in the mean percentage area change from baseline to 6 weeks. This means that if the lower limit of this confidence interval is greater than 12% non-inferiority will be established.

All the main efficacy analyses will be performed on the PP population. Complementary efficacy analyses will be performed on the ITT-population for further confirmation. The ITT and PP analyses will have to provide the same results to establish the non-inferiority. All safety analysis will be performed on the safety population.

Superiority can be concluded if the lower bound of a two sided 95% confidence interval for between-treatment differences (Exufiber® - Aquacel® Extra) in the mean percentage area change from baseline to 6 weeks does not overpass zero.

There will also be a second blinded assessment carried out (not using the PictZar system) that will support the main analysis done by PictZar.

For secondary variables Fishers exact test for dichotomous variables, Mantel-Haenszel chi-square test for ordered categorical variables and Pearson Chi-square test for non-ordered categorical variables and Fisher's non-parametric permutation will be used for continuous variables.

If necessary adjustment for baseline variables will be done with multiple logistic regression for dichotomous variables and with covariance analysis for continuous variables.

All statistical tests will be two-sided and conducted at the 5% significance level.

A sub-group analysis by country will be performed.

For the primary endpoint last observation carried forward will be applied for the final measurement. No other imputation methods will be used.

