#### 4.8.2 Determination of Sample Size

This investigation was designed to document the non-inferiority of the test dressing, Exufiber®, compared with the control dressing, Aquacel® Extra, on the relative reduction/change in wound size from baseline to end of investigation (6w). Applying a non-inferiority margin of 12% (same as EARTH investigation, Meaume et al 2014) and a standard deviation of 35%, 106 subjects were necessary in each group (i.e. 212 subjects in total) with a power level at 80%. Two investigations have been conducted on Exufiber®, one on DFU (diabetic foot ulcer) and one on PU (pressure ulcer). The SD are a little higher than 35% but since those investigations were quite small (21 subjects) it is reasonable to expect a smaller SD which justifies the calculation above.

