## 6. STATISTICAL METHODOLOGY AND SAMPLE SIZE DETERMINATION

### 6.1 General Methodology

In this non-inferiority study the primary efficacy analysis will be constructing a two sided 95% confidence interval, using Fisher's non-parametric permutation test, for between-treatment differences (Exufiber® - Aquacel® Extra) in the mean percentage wound area reduction from

baseline to 6 weeks follow-up. This means that if the lower limit of this confidence interval is greater than 12% non-inferiority will be established.

All the main efficacy analyses will be performed on the PP population. Complementary efficacy analyses will be performed on the ITT population for further confirmation. The ITT and PP analyses will have to provide the same results to establish the non-inferiority. All safety analysis will be performed on the safety population.

Superiority can be concluded if the lower bound of a two sided 95% confidence interval for between-treatment differences (Exufiber® - Aquacel® Extra) in the mean percentage wound area reduction from baseline to 6 weeks follow-up does not overpass zero.

There will also be a second blinded assessment carried out by an independent French expert (not using the PictZar system) that will support the primary efficacy analysis done by PictZar.

For comparison between the two randomized groups regarding baseline variables and secondary efficacy variables Fisher's non-parametric permutation will be used for continuous variables, Mantel-Haenszel chi-square test for ordered categorical variables, Pearson Chi-square test for non-ordered categorical variables and Fishers exact test will be used for dichotomous variables.

For continuous variables 95% confidence intervals based on Fisher's non-parametric permutation tests will be calculated for the mean differences between the two groups. For dichotomous variables 95% confidence intervals for difference in proportion will be calculated.

If significant differences are found in baseline variables between the two treatments, complementary analyses of treatment adjusted for these baseline variables will be performed. These adjustments for baseline variables will be done with multiple logistic regression analyses for dichotomous variables and with covariance analysis for continuous variables.

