## 6.5 Determination of Sample Size

This investigation was designed to document the non-inferiority of the test dressing, Exufiber®, compared with the control dressing, Aquacel® Extra, on the relative reduction/change in wound size from baseline to end of investigation (6w). Applying a non-inferiority margin of 12% (same as EARTH investigation, Meaume et al 2014) and a standard deviation of 35%, 106 subjects were necessary in each group (i.e. 212 subjects in total) with

a power level at 80%. Two investigations have previously been conducted on Exufiber®, one on diabetic foot ulcer and one on pressure ulcer. The SD are a little higher than 35% but since those investigations were quite small (21 subjects) it is reasonable to expect a smaller SD which justifies the calculation above.

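### The non-inferiority rule has lost its minus sign: all three statements ask for a lower 95% limit above +12%, so an equivalent dressing would fail the primary endpoint if the rule were applied as written

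*SAP*

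**What the plan says.** The non-inferiority criterion appears three times.

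- Protocol 4.8.1: "This means that if the lower limit of this confidence interval is greater than 12% non-inferiority will be established".
- SAP 6.1: "if the lower limit of this confidence interval is greater than 12% non-inferiority will be established".
- SAP 6.3.1, which applies it to the PP and ITT intervals together: "If the lower limits of both these confidence intervals are greater than 12% non-inferiority will be established".

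In each place the interval is a two-sided 95% confidence interval for Exufiber minus Aquacel Extra. The SAP defines the variable as percentage wound area reduction. Protocol 4.6.4 also defines the primary endpoint as a reduction, but Protocol 4.8.1 words the comparison as area change and gives no sign convention.

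The sample size sections treat 12% as a margin. Protocol 4.8.2 begins its calculation with "Applying a non-inferiority margin of 12" per cent, and SAP 6.5 continues "and a standard deviation of 35%, 106 subjects were necessary in each group", for 80% power.

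The superiority rule uses the lower bound of the same interval. It requires that this bound, in the words of Protocol 4.8.1, "in the mean percentage area change from baseline to 6 weeks does not overpass zero". SAP 6.1 has "in the mean percentage wound area reduction from baseline to 6 weeks follow-up does not overpass zero". SAP 6.3.1 applies the rule to the ITT population.

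**The concern.** On a scale where a positive difference favours Exufiber, a 12-point non-inferiority margin means that the new dressing may be up to 12 points worse. The lower limit should therefore be compared with -12. Comparing it with +12 asks for evidence that Exufiber is better by more than 12 points. That is stricter than the superiority rule, which compares the same bound with zero. A plan in which superiority can be shown while non-inferiority is missed is not coherent.

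This is the decision rule for the primary endpoint of a trial that, by Protocol section 1, supports a reimbursement application. Neither document contains a correct version to fall back on. If the sign were corrected only after results were known, the sponsor would be replacing a criterion that its data would almost certainly fail, and the change could look data-driven.

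Two wording faults sit in the same sentences:

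- The superiority phrase probably means that the interval does not cross zero. Read literally, as a lower bound that does not exceed zero, it is the reverse of superiority.
- The area change wording in Protocol 4.8.1 leaves the direction of benefit undefined.

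**Working it through.** **Inputs.** Margin 12 points, SD 35, 106 per group and power 80% (Protocol 4.8.2, SAP 6.5). Two-sided 95% interval (Protocol 4.8.1, SAP 6.1 and 6.3.1). The assumed true difference and the alpha behind the sample size are not stated. I take a true difference of 0 and use a normal approximation. D is the true difference in mean percentage reduction, Exufiber minus Aquacel Extra.

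**The plan's own figure.** n per group = 2 × SD² × (z_α + z_β)² / margin².

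- One-sided 5%: 2 × 35² × (1.645 + 0.842)² / 12² = 105.2, rounded up to 106. This matches the plan.
- One-sided 2.5%, the level that a two-sided 95% interval implies: 134 after rounding up. This does not match.

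So 106 is what a test against a limit 12 points below zero, with D = 0, gives at one-sided 5%.

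**Precision at 106 per group.** SE = 35 × √(2/106) = 4.81. Half-width = 1.96 × 4.81 = 9.42.

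**Observed difference needed to pass.**

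- Limit +12, as written: 12 + 9.42 = +21.4 points.
- Limit -12: -12 + 9.42 = -2.6 points.

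**Probability of passing.** For a limit c, P = Φ((D − c)/SE − 1.96).

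| True D | As written (c = +12) | Superiority (c = 0) | Margin as intended (c = -12) |
|---|---|---|---|
| 0 | 0.0004% | 2.5% | 70.4% |
| +5 | 0.03% | 17.9% | 94.2% |
| +10 | 0.9% | 54.8% | 99.6% |
| +12 | 2.5% | 70.4% | 99.9% |
| +20 | 38% | 98.6% | over 99.9% |

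For 80% probability of passing the written rule, the true advantage would have to be 12 + (1.960 + 0.842) × 4.81 = 25.5 points. Under the -12 limit, a dressing truly 12 points worse passes with probability 2.5%, as it should.

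**Sensitivity to the SD.** The documents say that the SDs in two small earlier studies were a little above 35. Over an assumed range of 30 to 45, with D = 0 and 106 per group, the probability of passing runs from 0.0000006 to 0.00005 as written, and from 83% down to 49% with a limit of -12.

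**The area change wording.** If change in Protocol 4.8.1 is signed, with shrinkage negative, then a lower limit above +12 would show that Exufiber is worse by more than 12 points. An equivalent dressing (D = 0) still fails, with the same probability. Inserting a minus sign would not repair that version, because the upper limit would then have to lie below +12. The variable has to be fixed together with the sign.

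All these probabilities are for one analysis population. Requiring both PP and ITT to pass can only lower them at the same n.

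**The case against.** The strongest reply is that this is an obvious slip whose intent is recoverable. The design is called non-inferiority throughout, both documents call 12% the margin, and the superiority rule uses zero. An analyst would in practice use -12, and a later correction could be traced to text written beforehand. That stands as far as intent goes, and the near-zero pass probabilities describe literal application only. It does not remove the need to correct the rule, since a confirmatory criterion should not have to be inferred from another section.

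Four narrower points:

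- The sample size match does not by itself prove the sign. The formula depends only on the distance between the true difference and the limit, so a limit of +12 with a true difference of +24 also gives 105.2. This is correct. The word margin carries the argument, and the arithmetic is only consistent with it.
- The smallest probabilities are normal-tail values for a permutation-based interval on an outcome that cannot exceed 100% reduction. They should be read as practically zero, not as precise figures.
- A minus sign could have been lost when the text was read from PDF. This cannot be fully excluded and can be checked against the signed files. It is unlikely, because the wording recurs three times across two documents with no gap, and the minus between the two product names survives in the same paragraphs.
- Under a signed reading of change, the Protocol sentence does not demand superiority by 12 points. That is so, but an equivalent dressing fails it under either convention.

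**Conclusion.** The concern holds. The rule as written is wrong in all three places, and no other text in either document corrects it. On the plan's own SD and sample size, literal application moves the required observed difference from -2.6 to +21.4 points. It cuts the chance that a truly equivalent dressing passes from 70.4% to practically zero, and this conclusion holds over the assumed SD range of 30 to 45. It rests on the normal approximation, 106 evaluable subjects per group and one analysis population.

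The 70.4%, short of the planned 80%, comes from a separate mismatch: 106 per group fits one-sided 5%, whereas the planned interval implies one-sided 2.5%. Correcting the sign neither causes nor cures that shortfall.

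**What to change.** Amend Protocol 4.8.1, SAP 6.1 and SAP 6.3.1 to carry one identical definition and rule:

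- D is the difference in mean percentage wound area reduction from baseline to 6 weeks, Exufiber minus Aquacel Extra; positive values favour Exufiber.
- Non-inferiority is concluded if the lower limit of the two-sided 95% confidence interval for D is above -12 percentage points in both the PP and the ITT population.
- Superiority is concluded if that lower limit is above 0 in the ITT population, which SAP 6.3.1 already names.
- In Protocol 4.8.1, area change becomes area reduction.

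The cost is a wording amendment to both documents, made and dated before database lock. Under Protocol 4.9 the Protocol part may need ethics committee notification or approval and, in many countries, that of the competent authority. The correction itself changes no visits, data collection or sample size; the power shortfall noted above should be dealt with as its own point.

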### **5.3 Efficacy variables**

#### **5.3.1 Primary Efficacy Endpoint**

Primary efficacy variable is relative reduction of wound area (%) from baseline to end of investigation (up to 6 weeks) measured by the validated system PictZar on the photos taken after debridement at week 0, week 4 and week 6 (or final visit).

A supportive primary efficacy variable will be the relative reduction of wound area (%) from baseline to end of investigation (up to 6 weeks) with measurements from the supportive blind review done by an independent French expert.

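### The superiority criterion is ambiguous: read literally it is inverted on the reduction scale, and the protocol applies it to an area change whose sign is undefined

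*SAP*

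**What the plan says.** The superiority rule appears three times.

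- Protocol 4.8.1 begins it with "Superiority can be concluded if the lower bound of a two sided 95% confidence interval for between-treatment differences", taken as Exufiber minus Aquacel Extra, and ends it with "in the mean percentage area change from baseline to 6 weeks does not overpass zero". It names no analysis population for superiority.
- SAP 6.1 has the same rule on a different variable: "in the mean percentage wound area reduction from baseline to 6 weeks follow-up does not overpass zero". It also names no population.
- SAP 6.3.1 repeats the SAP wording and adds the measurement tool and the population: "follow-up using PictZar on the ITT population does not overpass zero".

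Both documents define the primary endpoint as a reduction. Protocol 4.6.4 has "Relative reduction of wound area (%) from baseline to end of investigation (up to 6 weeks", and SAP 5.3.1 has "Primary efficacy variable is relative reduction of wound area (%) from baseline to end of investigation (up to 6 weeks". The sample-size text uses both words at once: protocol 4.8.2 has "on the relative reduction/change in wound size from baseline to end of investigation (6w", and SAP 6.5 matches it. Neither document gives a formula for the percentage, a sign for the change, or a meaning for 'overpass'.

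**The concern.** On a reduction scale, larger is better. A positive difference favours Exufiber, and superiority needs the lower confidence limit to lie above zero. The rule instead says what the lower limit must not do, using a verb whose plain sense is 'go beyond' or 'exceed'. Taken that way, a lower limit at or below zero satisfies the rule, which is the opposite of what a superiority claim needs. Where the same sections want a limit to lie above a value, in the non-inferiority rule, they use an ordinary greater-than comparison, so the change of verb is noticeable.

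The protocol adds a second uncertainty. If change is week 6 minus baseline, a healing wound has a negative value, and a difference above zero means that Exufiber wounds shrank less.

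This is the decision rule for a formal claim in an open trial. If its direction and scale have more than one reading when the data are analysed, a superiority conclusion can be challenged as interpretation after the fact.

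**Working it through.** **Inputs.** SD 35 percentage points, 106 subjects per group, margin 12 and power 80% (protocol 4.8.2, SAP 6.5); two-sided 95% interval (protocol 4.8.1, SAP 6.1 and 6.3.1). The plan states no true difference for superiority, so a range is shown.

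**The plan's own figure.** The superiority rule has no stated operating characteristic. The sample size that supplies the inputs is n = 2 × [35 × (1.645 + 0.842)/12]² = 105.2, so 106 per group at one-sided 5%. With 1.960, as the two-sided 95% interval implies, it would be 134 per group, and power at 106 would be 70.4%. That is a separate matter; only the SD and n are used below.

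**Standard error.** SE = 35 × √(2/106) = 4.81. Half-width = 1.96 × 4.81 = 9.42.

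**Formulas.** Let d be the true difference in percentage area reduction, positive when Exufiber is better.

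- 'Exceed' reading on reduction (lower limit at or below 0): P = Φ((9.42 − d)/4.81).
- 'Cross' reading on reduction (lower limit stays above 0): one minus that.
- On change signed so that healing is negative, replace d by −d.

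For the 'exceed' reading on reduction:

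- d = 0: Φ(1.96) = 0.975
- d = −12: Φ(21.42/4.81) = Φ(4.46), above 0.999
- d = +12: Φ(−2.58/4.81) = Φ(−0.54) = 0.296
- d = +15: Φ(−5.58/4.81) = Φ(−1.16) = 0.123
- d = +20: Φ(−10.58/4.81) = Φ(−2.20) = 0.014

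Probability that the rule is met:

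| Scale and reading | d = −12 | d = 0 | d = +12 | Result |
|---|---|---|---|---|
| Reduction, 'exceed' | >0.999 | 0.975 | 0.296 | inverted |
| Reduction, 'cross' | <0.001 | 0.025 | 0.704 | correct test |
| Signed change, 'exceed' | 0.296 | 0.975 | >0.999 | invalid, not inverted |
| Signed change, 'cross' | 0.704 | 0.025 | <0.001 | inverted |

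The SAP states its rule on reduction, so only the first two rows apply to it. The protocol falls under the last two rows if its change is signed, and under the first two if it means reduction. On signed change a correct rule would require the upper limit to be below zero. A rule on the lower limit cannot deliver that under either meaning of the verb.

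**The case against.** The strongest reply is that 'overpass' can mean 'cross', and that the surrounding text favours this. The rule names the lower limit on a higher-is-better scale, which is where a standard superiority test looks. Protocol 4.8.1 and SAP 6.1 set all tests at a two-sided 5% level; a rule met 97.5% of the time at equality contradicts that, while the 'cross' reading satisfies it. An experienced analyst would probably program the correct test from the SAP. This stands, and it is why the point is ambiguity and not a settled error of direction. It does not remove the need for a correction. The neighbouring non-inferiority rule prints its 12% limit without a minus sign, so the adjacent text is a poor guide to sign, and under signed change the protocol rule fails on either reading.

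Three stronger inferences are not supported.

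- A reader might infer that, as written, a worse dressing qualifies as superior in both documents. No single reading of the verb inverts both if the protocol's change is signed. The literal reading inverts both only if change already means reduction, and then there is no scale mismatch.
- A reader might infer that the sign of the scale is left open until data are seen. The endpoint definitions and every SAP decision rule say reduction, protocol 4.8.1 leaves analysis details to the SAP, and a blinded observer measures the wound areas (protocol 4.7.3).
- A reader might infer that a superiority claim is meant for the reimbursement file. The protocol Introduction says that the investigation supports a renewal application; it does not mention superiority there.

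**Conclusion.** The concern holds as one of ambiguity. The superiority criterion has two readings, and the literal one is inverted on the SAP's reduction scale: it is met 97.5% of the time when the dressings are equal, over 99.9% when Exufiber is 12 points worse, and 12% when it is 15 points better. The other reading is the correct test in the SAP, met 2.5% of the time at equality and 70.4% at +12 points. In the protocol, if change is signed so that healing is negative, neither reading is valid.

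The probabilities use a normal approximation to the permutation-based interval, a common SD of 35, and 106 analysed subjects in each group. They describe each reading of the rule and do not predict what the analyst would do. The sentence governs a formal conclusion, so it should have one meaning before the data are analysed.

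**What to change.** Make the same correction in protocol 4.8.1, SAP 6.1 and SAP 6.3.1:

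1. Define percentage area reduction = 100 × (baseline area − week-6 area)/baseline area, with positive values meaning healing.
2. State that superiority is concluded if the lower limit of the two-sided 95% confidence interval for Exufiber minus Aquacel Extra in mean percentage area reduction, in the ITT population, is greater than 0. SAP 6.3.1 already names that population; the other two places need it added.
3. Delete 'change' and the 'overpass' wording.

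For consistency, protocol 4.8.2 and SAP 6.5 could drop the paired reduction/change wording too. Making superiority conditional on non-inferiority is optional and not needed for this correction.

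The cost is wording in the SAP and the protocol. The sample size, the data collected and the interval method do not change. Under the corrected rule, superiority is declared with probability 0.025 at equality, 0.704 at +12 points and 0.986 at +20 points.
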